Lastly, preliminary data also suggest greater levels of plasma inflammatory mediators in subjects with a PFO and systemic inflammation is associated with increased risk of cardiovascular diseases. Importantly, exercise is known to reduce so of these systemic inflammatory mediator levels. Thus, PFO/ASD closure may allow for greater exercise capacity and a subsequent reduction in inflammation.

Thus, although a PFO has been traditionally considered to have a minimal impact of physiology and pathophysiology, emerging evidence suggests this may not be the case. Our lab is focused on understanding how and why a relatively small hole in the heart (PFO/ASD) can have a relatively large impact on cardiopulmonary and respiratory physiology.

B. Specific Aims/Study Objectives

The overarching goal of this study is to examine cardiopulmonary and respiratory physiology pre and post PFO/ASD closure in patients who are undergoing surgical closure of their PFO/ASD.

Pre and post PFO/ASD closure, we will:

- 1) Quantify pulmonary gas exchange efficiency (alveolar to arterial O2 difference) and arterial oxygenation at rest and during exercise.
- 2) Quantify aerobic exercise capacity, daily activity, six-minute walk test.
- **3**) Quantify Q_{IPAVA} at rest and assess recurrence of stroke or TIA at 3 months.
- **4)** Quantify plasma inflammatory markers (TNFa, IL-1, 6 & CRP)
- **5)** Measure hypercapnic ventilatory response
- **6)** Quantify core body temperature

Hypotheses: We hypothesize that closure of PFO/ASD will improve pulmonary gas exchange efficiency, improve exercise capacity, and reduce blood flow through PFO/ASD and IPAVA thereby preventing subsequent stroke. PFO/ASD closure will also reduce plasma inflammatory mediators, increase ventilation in response to a hypercapnic challenge, and will result in a lower core body temperature.

C. Methods, Materials and Analysis

This study will be performed over the course of 7 days at the Cardiopulmonary and Respiratory Physiology Lab at the University of Oregon. Days 1-3 are Pre-PFO/ASD closure procedure and Days 4-7 repeat all research activities beginning at 3 months post PFO/ASD closure procedure. Those cleared for exercise by their cardiologists (see recruitment below)

will participate in all aspects of the study, Days 1-7. Those *not cleared for exercise* by their cardiologists will participate in all non-exercise aspects of the study Days 1-4 [gray highlight for non-exercise subject information].

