Special note on post PFO/ASD closure procedures: The timing of post PFO/ASD closure procedure visits were carefully selected (i.e., 3 and 6 months) based on recommendations from the referring physicians ([name] and [name]). It is their collective recommendation that 6 months (and in some cases 3 months) is sufficient to allow for physical closure/endothelialization of the PFO/ASD. However, if is it determined at 6 months post PFO/ASD closure procedure that the PFO/ASD has been deemed NOT PHYSICALLY CLOSED/ENDOTHELIALIZED by the referring physician, the subject will not partake in the post-closure visit(s) scheduled at 6 months, AND they will be excluded from the study.

Screening at each study visit: Female subjects will be required to take a urine pregnancy test before each visit begins. A positive test at anytime will result in exclusion. A Modified Allen's test will be performed on Day 1 for all subjects and during each day when an arterial line is placed. Failing the Modified Allen's test at anytime will result in exclusion.

Protected Health Information (PHI): Participating Physicians [name] and [name] will provide PHI to the investigators. The PHI provided will include: the reason(s) for PFO/ASD closure procedure (e.g., TIA, Stroke, dyspnea upon exertion, etc.), when the PFO/ASD has physically closed/endothelialized per referring physician (e.g., at 3 or 6 months), current and past medication information, and results from clinical exercise studies as they pertain to determining the reason(s) for closure (e.g., arterial oxygen saturation at rest and during exercise, rating of perceived exertion, etc). Subjects will be asked to sign a HIPAA authorization form on Day 1. The PHI will be used for research purposes only. Of note, this information is only solicited via self-report from those who have reported a prior history at the time of enrollment.

The following Figures (i.e., 1 & 2) are meant to assist in determining the path through the study days, and should be used in conjunction with the detailed study-day descriptions.

This portion left intentionally blank

Figure 1. Exercise

[figure not shown]
[figure not shown]

Figure 2. Non-Exercise

EXERCISE SUBJECTS

What follows is a detailed description of the study days. For convenience, please refer to Figure 1. Exercise (page 4) to assist in determining the timing of study days.

Visit 1 Pre PFO/ASD Closure Procedure (~2.5hrs) AND:

Visit 4a (PFO/ASD Physically Closed/Endothelialized) (~2 hours) OR,

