Visit 4b (PFO/ASD Not Physically Closed/Endothelialized) (~30 min)

Visit 4a (If PFO/ASD is **physically closed/endothelialized** at 3 months per referring physician)

Subjects will undergo informed consent, fill out health history questionnaire, sign a HIPAA authorization form and perform a Modified Allen's Test (~45 min)

Subjects will be comprehensively screened for any cardiac abnormalities. Amount of blood flow travelling through the PFO/ASD and IPAVA will be graded using saline contrast echocardiography while the subject is breathing room air (PFO/ASD and IPAVA blood flow) and breathing 100% O2 (PFO/ASD blood flow only). Pulmonary artery pressure will also be measured using ultrasound. Intravenous blood draw, we will take 21mls (~2 Tablespoons) of iv blood (~1.25 hrs)

Subjects will perform pulmonary function, plethysmography and diffusing capacity (30min)

Visit 4b (If PFO/ASD is **not physically closed/endothelialized** at 3 months per referring physician)

Subjects will receive and intravenous blood draw, and we will take 21mls (~2 Tablespoons) of IV blood (30 min).

Visit 2 Pre PFO/ASD Closure Procedure (~2.5 hrs) AND:

Visit 5a (PFO/ASD Physically Closed/Endothelialized) (~2.5 hrs) OR,

Visit 5b (PFO/ASD Not Physically Closed/Endothelialized) (~2 hrs):

Visit 5a (If PFO/ASD physically closed/endothelialized) at 3 months per referring physician)

Subjects will undergo a hypercapnic breathing challenge (~1hr)

Subjects will be given an activity monitor and given instructions on how and when to use it (~30 min) (Detailed Instructions on Visit 2 ONLY. On Visit 5, they will be reminded of the instructions, with details as required)

Subjects will perform a 6 minute walk test (~15 min)

Subjects will perform a VO2max test (~30 min)

Visit 5b (If PFO/ASD **not physically closed/endothelialized** at 3 months per referring physician)

Subjects will undergo informed consent, fill out health history questionnaire, sign a HIPAA authorization form and perform a Modified Allen's Test (~45 min)

Subjects will be comprehensively screened for any cardiac abnormalities. Amount of blood flow travelling through the PFO/ASD and IPAVA will be graded using saline contrast echocardiography while the subject is breathing room air (PFO/ASD and IPAVA blood flow) and breathing 100% O2 (PFO/ASD blood flow only). Pulmonary artery pressure will also be measured using ultrasound. Intravenous blood draw, we will take 21mls (~2 Tablespoons) of iv blood (~1.25 hrs)

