• Modified Allen's Test (Days 1, 3 & 6a OR 7b Exercise; Days 1, 2 & 3a OR 4b NON-Exercise):

This test examines collateral blood flow in the hand, and is performed on the first day and each day there is an arterial line placed. The subject clenches their fist for ~30 seconds while the radial and ulnar arteries are occluded by the investigator. The ulnar artery is released and the return of circulation (color to the hand) is examined. If the color doesn't return, then this is considered a negative test (fail). Both hands will be tested, two failures (right and left hand) is exclusionary.

• Comprehensive ultrasound screening (Days 1 & 4a OR 5b Exercise; Days 1 & 3a OR 4b NON-Exercise):

An intravenous catheter will be placed in the subject. Subjects will sit in the left lateral decubitis position for ultrasound screening. An agitated saline contrast injection will be made while transthoracic saline contrast echocardiography (TTSCE) is performed on the subject to evaluate extent of blood flow through IPAVA and PFO/ASD. This will be repeated while breathing 100% O2 for 10 minutes. Subject will be asked to perform a Valsalva maneuver while breathing room air and 100% O2. This maneuver enhances blood flow across the PFO/ASD. Multiple saline contrast injections (up to 3) may be performed to verify bubble grades/presence of a PFO/ASD.

Pulmonary Function Tests (Days 1 & 4a OR 5b Exercise; Days 1 & 3a OR 4b NON-Exercise):

• Subjects will perform standard non-invasive spirometry to measure a maximal inspiratory and expiratory flow-volume loop, forced vital capacity (FVC), forced expiratory volume in 1 sec (FEV1), and mid expiratory flow (FEF25-75%). These tests will require the subject to blow in and out of a mouthpiece connected to a computerized flowmeter (pneumotachometer). This is a routine clinical test performed in pulmonary function labs in the United States.

• Diffusing Capacity (DLCO) (Days 1 & 4a OR 5b Exercise; Days 1 & 3a OR 4b NON-Exercise):

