Echocardiography requires a medical sonographer from PeaceHealth to place a small probe against the subject's ribcage, which transmits and receives sound waves to produce images that are captured and stored on a computer. Saline contrast is made by manually agitating (mixing) 3-5 ml of sterile saline and 1 ml of air to create a suspension (mixture of liquid and gas) of very small bubbles called microbubbles. This suspension is injected through an IV, which allows us to detect the transpulmonary passage of microbubbles.

• Intravenous Catheter (IV) (Days 1,3,4a OR 4b, 5b, 6a, 7a OR 7b Exercise; Days 1-3a, 4a OR 4b NON-Exercise):

We will place a 20-22 gauge (small diameter) IV into a vein in the subject's arm that will be used for the rapid injection of the agitated sterile saline for TTSCE during Days 1,3,4a OR 4b, 5b, 6a, and 7a OR 7b Exercise; Days 1-4 NON-Exercise. This catheter will also be used to measure plasma inflammatory mediators. Blood will be centrifuged and de-identified plasma stored at -80°C until assayed by ELISA kit. Total IV blood draw is approximately 63 mL for exercise or non-exercise participants.

• Hypercapnic ventilatory response (Days 2 & 4a OR 5b Exercise; Days 2-3a OR 4b NON-Exercise):

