Prior to catheter placement the physician will perform a modified Allen's Test to confirm adequacy of collateral circulation of the hand. A physician ([name]) will perform catheterization of the radial artery. Using a standard, sterile procedure [name] will place a small catheter into the radial artery (arterial catheterization). [name] will initially numb the wrist with lidocaine/nitroglycerin solution. Then [name] will place a needle into the radial artery. [name] will then place a small guide wire through the needle in to the vessel. Then he will place a flexible catheter into the vessel using the guide wire for direction. This catheter will be used to collect blood totaling <100 mL (< 7 Tablespoons) in the exercising subjects and < 25 ml (<2 Tablespoons) in resting subjects. Blood draws will be accompanied by a heparinized saline flush (1unit heparin/ml) to reduce chances of catheter clotting. 12 lead ECG, heart rate, metabolic, ventilation data will be continuously collected and arterial blood oxygen saturation will be continuously measured via a non-invasive transcutaneous forehead sensor.

*Note:

TOTAL blood draw for Exercise subjects (i.e., IV + Arterial Line) will be less than 250 mL. TOTAL blood draw for Non-Exercise subjects (i.e., IV + Arterial Line) will be less than 125 mL.

However, if it is deemed at 6 months by the referring physician that the PFO/ASD has not been physically closed/endothelialized, subjects will not partake in the scheduled 6-month post PFO/ASD closure procedure visits. Thus, the amount of blood drawn from these subjects would be significantly reduced. Specifically:

Exercise subjects without 6 month visits (i.e., total blood drawn): < 125 mL Non-exercise subjects without 6 month visits (i.e., total blood drawn): < 75 mL Risks and interventions to mitigate such are included in Section G.

• Exercise with arterial line (Days 3, 6a OR 7b Exercise subjects only):

After arterial line placement (see above) the subjects will perform two bouts of graded submaximal exercise tests on the cycle ergometer at 25%, 50%, 75% and 90% of their VO_{2max} with each stage lasting 4 minutes with up to 15 minute breaks between stages. During one bout, subjects will breathe normal oxygen levels (21% oxygen), during the other bout, subjects will breathe high oxygen levels (40% oxygen). Bouts will be randomized and separated by 30 minutes of rest breathing room air.

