D. Research Population & Recruitment Methods & Compensation

1-2. Sample size, Population and Recruitment Methods:

Sample Size and Data Analyses:

Necessary sample size was determined with our primary outcome variables ($AaDO_2$, VO_{2MAX} , saline contrast bubble scores, TNFa levels) using our preliminary data, previously published work and *a priori* power analysis. Using G-Power and information about a physiologically-meaningful effect from published studies (i.e. reduction of $AaDO_2$ by 50%, VO_{2MAX} increasing by 10% and 6 min walk test increasing by 50 meters (15, 34, 41)(24, 40)(24, 40), TNF-a levels decreasing by 50%, a desired power of 0.80, and alpha (0.05), we determined that n = 8-10 individuals would be sufficient to test our hypotheses, using a repeated measures design. Thus, we are asking to recruit 20 subjects (any combination of male and female) in the event

our actual pre-to-post changes are less than expected and/or there is greater variability than our preliminary data suggest.

Mean differences in $AaDO_2$ and core body temperature between pre- and post-PFO/ASD closure will be analyzed using a repeated measures ANOVA with Tukey posttest. Mean differences in $VO_{2MAX,}$ 6 minute walk test, activity, inflammatory markers and hypercapnic ventilator response, between pre and post PFO/ASD closure will be analyzed using a paired t-test. Differences in bubble scores pre- and post-closure will be analyzed using a Mann-Whitney U test.

The population of subjects will include patients who are undergoing PFO/ASD closure at either PeaceHealth or McKenzie-Willamette Hospitals. Subjects will be identified by [name] (PeaceHealth/Oregon Heart & Vascular Institute) and [name] (McKenzie-Willamette). These two cardiologists will only refer subjects to contact the [name] Lab for informed consent and enrollment into the study. Drs. [name] and [name] will identify potential subjects as "cleared for exercise" or "not cleared for exercise." (See statement of PHI above). Drs. [name] and [name] will not be formally engaged in the research (i.e. they will not consent subjects, have access to identifiable data, etc). No research activities will take place at either hospital. Subject fliers, initial phone script and email script are attached.

3. Detailed Recruitment information:

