Safety Monitoring: Subjects will be given clear instructions that they should notify the investigators immediately if they experience any of the above-mentioned risk symptoms. During all exercise and recovery procedures, all subjects will be non-invasively and continuously monitored for vital signs using: 1) a 12 lead EKG to monitor electrical activity of the heart, and 2) a forehead probe to monitor arterial oxygen saturation and heart rate. During all other procedures subjects will be visually monitored for any signs of discomfort, distress or problems. During both exercise and resting procedures, the investigators will continuously ask the subjects how they are feeling and how they are doing.

H. Potential Benefits of the Research

This study will not improve the health of subjects and is only being done to gather information. This study will not improve the health of the general subject population. Completing the aims of this study will have the benefit of contributing to generalizable knowledge.

I. Investigator Experience

The PI and colleagues have been performing cardiopulmonary and respiratory physiology investigations at rest and during exercise in healthy and diseased populations at the University of Oregon for ~10 years. [name] CV is on file.

The PI trains all graduate and undergraduate personnel on all laboratory procedures and protocols. Co-investigator [name] is a board certified cardiologist who has worked with [name] group for almost 10 years placing radial artery catheters, interpreting echoes and providing significant intellectual input to the laboratory group.

Ultrasound technicians, [name], RDCS and [name], RDCS have worked with [name] group for years as well ([name] ~10 years; [name] ~5 years). These two

registered diagnostic cardiac sonographers (RDCS) have performed thousands of resting and stress echoes in patients and research subjects.

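### Bubble scores are a primary outcome graded by eye in an open pre/post design, and no masked or random-order reading is described although the images are stored

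*Combined protocol and SAP*

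**What the plan says.** Section D (Sample Size and Data Analyses) lists "saline contrast bubble scores, TNFa levels" among the primary outcome variables, and plans a Mann-Whitney U test for bubble scores before against after closure.

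The visit descriptions in Section C state: "Amount of blood flow travelling through the PFO/ASD and IPAVA will be graded using saline contrast echocardiography". Room air is meant to show PFO/ASD and IPAVA flow together, and 100% oxygen to show PFO/ASD flow only. No grading scale or criteria are given.

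Under Comprehensive ultrasound screening: "Multiple saline contrast injections (up to 3) may be performed to verify bubble grades/presence of a PFO/ASD". Under Transthoracic Saline Contrast Echocardiography, the probe is described as one "which transmits and receives sound waves to produce images that are captured and stored on a computer".

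The Section B hypothesis is directional: closure will "reduce blood flow through PFO/ASD and IPAVA thereby preventing subsequent stroke". The special note in Section C restricts who gets full post-closure testing. If the defect is not deemed closed at 6 months, "the subject will not partake in the post-closure visit(s) scheduled at 6 months, AND they will be excluded from the study".

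Section I credits a cardiologist co-investigator with "placing radial artery catheters, interpreting echoes and providing significant intellectual input to the laboratory group". The only randomisation in the plan concerns the two exercise tests: "Bouts will be randomized and separated by 30 minutes of rest breathing room air". Masked reading, random reading order, a second reader and reader agreement are not mentioned.

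**The concern.** A bubble grade is a judgement on an ordinal scale. With no control group, every grade is either before or after closure, so a reader who knows the visit knows the very contrast under test. Knowing the gas matters too, because oxygen is what separates PFO/ASD flow from IPAVA flow.

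Grades are checked at the visit, since repeat injections may be made to confirm them. No rule says when to repeat or which injection supplies the analysed score.

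Any lean would favour the hypothesis. The IPAVA result is the more exposed. A fall in PFO/ASD grade is largely expected once full post-closure testing is limited to defects deemed closed. A fall in IPAVA grade is a separate claim that rests on the same clips, with no such anatomical reason behind it.

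**Working it through.** **1. What the documents establish and what is inferred**

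| Point | Status |
|---|---|
| Bubble score is a primary outcome | Stated (Section D) |
| Flow is graded from contrast echo | Stated (Section C, visit descriptions) |
| Grades are checked at the visit | Follows from repeat injections used to verify them |
| Images are stored | Stated (Section C, TTSCE) |
| Masking or random reading order | Not described anywhere |
| Who assigns the analysed score, and when | Not stated |
| Reader knows the visit | Inferred from the open pre/post design |

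**2. The plan's own figure.** Section D gives n = 8-10 as sufficient and 20 to be recruited, at power 0.80 and alpha 0.05. It states no effect size for bubble scores, and no SD or pre/post correlation for any outcome, so the figure cannot be reproduced. This point does not depend on it, and masked reading leaves it unchanged.

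**3. Size of a one-grade lean.** Assume no true change, and 6 of 20 subjects read one grade lower after closure.

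- Mean change = -(6 x 1)/20 = -0.30 grade, all of it bias.

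**4. The same lean under a paired test.** With all other subjects tied, only the 6 changes count, and all go the same way. The exact two-sided sign or signed-rank p-value is 2 x 0.5^k for k such changes:

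- k = 5: 2 x 0.5^5 = 0.0625
- k = 6: 2 x 0.5^6 = 0.031

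**5. The same lean under the planned Mann-Whitney test.** The result depends on how baseline grades are spread, which the documents do not give. In 4,000 random draws for each assumed range:

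| Assumed baseline grades | Median p | Draws with p < 0.05 |
|---|---|---|
| Spread over 1-5 | about 0.53 | none |
| Spread over 3-5 | about 0.33 | none |
| All identical | 0.009 | all |

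For identical baselines, 20 pre grades face 14 equal and 6 lower post grades.

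- U = 20 x 14 x 0.5 + 20 x 6 = 260, against a null mean of 20 x 20/2 = 200.
- Tie-corrected variance = (400/12) x [41 - (39,270 + 210)/1,560] = 523.1, so SD = 22.87.
- With continuity correction, z = 59.5/22.87 = 2.60 and p = 0.009.

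The test ignores pairing, so ordinary spread between subjects swamps a small shift within them.

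**6. Adding reading noise.** This simulation used 4,000 runs per setting. Assumptions: 0-5 scale, true grades evenly spread over 1-4, no true change, a one-grade random error in 20-40% of reads, and a fraction q of post-closure grades lowered by one. False-positive rates at n = 20:

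| q | Paired signed-rank | Mann-Whitney |
|---|---|---|
| 0 | about 0.04 | below 0.01 |
| 10% | 0.06-0.07 | below 0.01 |
| 20% | 0.12-0.19 | below 0.01 |
| 30% | 0.22-0.34 | below 0.01 |

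Masked reading aims at q = 0. The documents give no value for q.

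**The case against.** **The visit may not be known to the reader.** A reader might infer that scores are graded with the visit known. The documents do not say so: they name no reader for the analysed score and do not say when it is assigned. Section I describes the co-investigator's work for the laboratory in general. The inference is strong, because grades are checked at the visit, but the supportable statement is that no masking is described.

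**Six leaning grades may not produce a false positive.** A reader might infer that they would. Under the stated Mann-Whitney analysis they generally would not, as step 5 shows. Step 4 also assumes that every other subject is exactly tied. This objection stands as far as the p-value goes. It does not remove the bias in the estimated change, and a move to a paired test would bring the false-positive risk back.

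**Masking may protect the PFO/ASD grade little.** Open or closed anatomy, or a device, may itself show which visit a clip comes from. The documents do not address visibility, so the extent is unknown. This stands in part. Even where pre/post is revealed, gas, stage and subject can stay hidden. Exercise subjects alone supply 4 stages x 2 bouts x 2 periods = 16 exercise gradings each, which makes recall of individual clips harder.

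**Repeat injections may be innocent.** They are allowed in order to confirm a grade, and nothing shows that they would be used in a biased way. That is fair. What remains is that no rule says which injection counts.

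**Conclusion.** The point holds as a cheap improvement. A primary outcome is graded by a person, in an open single-group comparison with a directional hypothesis. The plan describes no masking or random reading order, although the stored images would allow both.

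The main consequence is possible bias in the estimated change, towards lower post-closure grades and above all for IPAVA flow. A one-grade lean in 30% of subjects (6 of 20) moves the mean by 0.30 grade. It would generally not give p < 0.05 under the planned test, but could under a paired test: p = 0.031 with all others tied, or a false-positive rate of 0.22-0.34 with the assumed reading noise.

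These sizes rest on assumed amounts of bias, noise and baseline spread. The documents do not show that any bias will occur.

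**What to change.** Take the analysed bubble score from a reading of all stored clips after data collection ends, by an existing study reader named in advance. Read in random order, with subject, date, pre/post, inspired gas and exercise stage hidden. State the grading scale.

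Fix in advance which of the repeat injections supplies the score, and store every injection. Masked reading cannot undo choices made while the images were being acquired, so this rule is needed as well.

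Have the reader record whether a device or the closure was visible, and report this as a limitation. Do not exclude those clips: they would be mainly post-closure, and dropping them would break the pairs.

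The cost is the work of coding and shuffling clips. No extra subject, visit or procedure is needed, and the sample size is unchanged. The remaining weakness is incomplete masking where closure can be seen.

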• Intrapulmonary & intracardiac Shunting with arterial line placement (Days 3, 6a OR 7b Exercise subjects; Days 2-3a OR 4b NON-Exercise subjects):

Saline contrast echocardiography will be performed during the third minute of each exercise stage to assess intrapulmonary and intracardiac shunting. Saline contrast echocardiography will also be performed in NON-exercise subjects at rest.

 Measurement of core body temperature (Days 3, 6a OR 7b Exercise subjects; Days 2-3a OR 4b NON-Exercise subjects):

An esophageal temperature probe (Nelcor used with Mon-a-Therm System) will be placed. We will be using esophageal temperature monitoring because core temperature is a primary outcome variable of this study and esophageal temperature is considered to be the gold standard technique for measuring core temperature during short duration exercise testing. We also use this temperature to correct our blood gas values. In order to place the esophageal probe, subjects will be given lidocaine Jelly (2% lidocaine, 1 ml intranasal administration). After administration of the lidocaine Jelly, researchers will place the esophageal probe through one of the nostrils, and advance the probe until it is visible in the back of the throat. Once the probe is visible, the subject will then begin to sip water through a straw while the researcher advances the probe to the appropriate depth. The swallowing of the water helps to insure that the probe goes down the esophagus and not the trachea. Researchers will make no more than 2 attempts per nostril to place the esophageal probe. In the event subjects cannot tolerate the esophageal temperature probe, subjects will swallow an ingestible pill, about the size of a multi-vitamin, that is designed for human use (FDA approved) and is accurate to 0.1°C (CoreTemp, HQI Technologies, Inc.). This pill will be used to measure core body temperature at rest and during cycle ergometer exercise. Prior to ingestion the temperature pill will be calibrated with an external wireless recording device. This will allow us to wirelessly acquire the subjects core temperature when necessary as the temperature pill transmits a signal to the external device that will then display the appropriate temperature. This pill will harmlessly pass through the subject's intestinal tract. The pill is not recovered, is disposable, and every subject receives a new pill for each study day.

Table 1 – Exercise

Group - Exercise											

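### Four outcomes are called primary in one section and a fifth in another, with a single alpha of 0.05, no rule across them, no single deciding comparison for four of the five, and no set number of exercise subjects

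*Combined protocol and SAP*

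**What the plan says.** Section D, Sample Size and Data Analyses, opens with "Necessary sample size was determined with our primary outcome variables" and names AaDO2, VO2max, saline contrast bubble scores and TNFa. In section C, the paragraph on core body temperature states that "core temperature is a primary outcome variable of this study". The only error level is in the sample-size sentence: "a desired power of 0.80, and alpha (0.05", leading to n = 8-10. Then "we are asking to recruit 20 subjects (any combination of male and female", with no split between exercise and non-exercise subjects.

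The same section assigns a method to every outcome, each as a pre/post comparison: repeated measures ANOVA with Tukey for AaDO2 and core temperature, paired t-test for VO2max and inflammatory markers, and Mann-Whitney U for bubble scores.

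The data behind those tests are wider than one pre and one post value:

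- **TNFa.** "Total IV blood draw is approximately 63 mL for exercise or non-exercise participants", at 21 mL per draw.
- **AaDO2.** Aim 1 reads "Quantify pulmonary gas exchange efficiency (alveolar to arterial O2 difference) and arterial oxygenation at rest and during exercise".
- **Bubble scores.** At the ultrasound screening, "Subject will be asked to perform a Valsalva maneuver while breathing room air and 100% O2"; injections are also made at each exercise stage.
- **Exercise measurements.** "Exercise with arterial line (Days 3, 6a OR 7b Exercise subjects only". The VO2max test is likewise confined to exercise subjects. Table 3 leaves the choice of group to the subject's physician.

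**The concern.** Two sections of the same plan disagree on how many primary outcomes there are, and neither says how many must succeed for the closure hypothesis to be supported. Tukey works only inside the two ANOVAs, so nothing covers the set of primaries as a whole.

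Within most primaries, the visit or condition that decides the answer is also open and could be settled after the data are seen. A reader of the results could then not tell a planned finding from a selected one.

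Separately, n = 8-10 is offered as sufficient for outcomes that include VO2max. Nothing in the plan ensures 8-10 exercise completers among the 20, and subjects whose defect is not deemed closed at 6 months are excluded.

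**Working it through.** **1. The plan's own figure.** n = 8-10 cannot be reproduced forwards, because no SD of change is given for any outcome and sidedness is not stated. It can be solved backwards. For a paired t-test with n pairs, power is P(|T| > t crit), where T is noncentral t with n-1 df and noncentrality dz x sqrt(n). The dz giving 80% power at alpha 0.05 is:

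| | n = 8 | n = 10 |
|---|---|---|
| two-sided | 1.156 | 0.996 |
| one-sided | 0.978 | 0.853 |

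**2. Comparisons left open.**

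- TNFa: 63/21 = 3 draws, one before closure and two after. Exercise subjects have Visits 1, 4a and 7a, or 1, 4b and 5b; non-exercise subjects have 1, 3a and 4a, or 1, 3b and 4b. One paired t-test is planned and the post draw is not named.
- AaDO2 and temperature: 1 rest + 4 stages x 2 oxygen levels = 9 conditions in exercise subjects, rest only in the others. The ANOVA factors and the deciding contrast are not given.
- Bubble scores: room air, 100% O2, Valsalva, exercise stages and two shunt sites. Aim 3 specifies IPAVA flow at rest, but the hypothesis also covers flow through the PFO/ASD.
- VO2max: one pre and one post value, so this one is defined.

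**3. False positives if any one primary counts** (assumed rule; one two-sided test per outcome at 0.05).

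- Independent: 1 - 0.95^4 = 0.185 and 1 - 0.95^5 = 0.226.
- Equal correlation (assumed; normal simulation, 1,000,000 draws): at 0.5, 0.156 and 0.18; at 0.7, 0.131 and 0.15.

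**4. Power if all primaries must succeed** (0.80 each).

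- Independent: 0.8^4 = 0.410 and 0.8^5 = 0.328.
- Correlation 0.7: 0.62 and 0.59.

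**5. What a five-way split does to paired-t power.** The first Holm step with five primaries is 0.05/5 = 0.01; with four it is 0.05/4 = 0.0125. Two-sided power at 0.01, over the back-solved dz:

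| completers | dz 1.00-1.16 | dz 0.85-0.98 |
|---|---|---|
| 10 | 0.50-0.66 | 0.36-0.48 |
| 20 | 0.93-0.98 | 0.82-0.92 |

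The dz detectable with 80% power at n = 20 is 0.66 at 0.05, 0.82 at 0.0125 and 0.84 at 0.01. These are paired-t figures. They do not carry over to the ANOVA or bubble-score outcomes, and the plan does not tie the back-solved dz to any one outcome.

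**The case against.** This is a small physiological study with six aims and an outcome-specific prediction for most of them. Section D speaks of hypotheses in the plural, and section H says the work is done to gather information. Testing separate hypotheses each at 0.05, with no overall claim, is a legitimate design, and under it there is no family-wise error to correct. That stands: the 13-23% figures depend on an any-one-counts rule that the plan never states. But the plan does not state the separate-hypotheses rule either, and it does label the outcomes primary.

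Three stronger readings are tempting, and the documents do not support them.

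- *The primaries have no defined test.* A method and a pre/post contrast are given for every one. What is missing is the visit, condition or shunt site. A repeated measures ANOVA can hold several stages in one model, so nine conditions do not mean nine tests.
- *Twenty subjects are too few.* For paired-t outcomes measured in all 20, power at alpha 0.01 is 0.82-0.98 at the back-solved dz. The exposure is the unknown size of the exercise group.
- *Stating the exercise number would settle power.* It would not, because no SD is given.

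**Conclusion.** The concern holds as a conflict over the primary list, a missing rule across outcomes, and an open deciding comparison for four of the five. It is more than missing detail, because the two sections contradict each other and unadjusted testing of four or five primaries can raise the false-positive risk to between 2.6 times (0.131/0.05) and 4.5 times (0.226/0.05) the nominal level.

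That size assumes that any one success counts, one test per outcome, and correlations between 0 and 0.7; the open comparisons could raise it further. Under an all-must-succeed rule the problem is instead low joint power, 0.33 to 0.62 over the same range. Under separate hypotheses with no overall claim neither figure applies, but the conclusions would have to be limited accordingly.

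Power for VO2max and exercise AaDO2 cannot be checked from the plan, since both the number of exercise completers and the SDs are absent. The sponsor should correct this; it does not show that the study is undersized.

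**What to change.** 1. Reconcile the core temperature paragraph in section C with section D to give one primary list. Label the rest secondary, with nominal p-values.
2. Give each primary one deciding comparison and hold family-wise error at two-sided 0.05 by Holm or a pre-stated fixed order. If the sponsor intends separate hypotheses each at 0.05, or that all must succeed, state that rule and limit the conclusion to match.
3. Name the comparisons.
   - TNFa: Visit 1 against a draw at a common time in all subjects, for example the later draw (7a or 5b exercise; 4a or 4b non-exercise). This is taken here as the 6-month draw, to be confirmed against Figures 1 and 2; by then every retained subject has been deemed closed. Using the draw at the post-closure echo visit instead would mix 3-month and 6-month samples by closure status. The other draw is secondary.
   - AaDO2 and core temperature: either rest (all subjects) or the pre/post main effect over stages (exercise subjects only).
   - Bubble scores: one shunt site and one condition, with a paired test, because the same subjects are measured twice and Mann-Whitney U treats the two sets as independent.
4. Restate the sample-size sentence separately for 20 subjects and for the expected exercise completers, with the sponsor's SDs and sidedness.

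**Cost.** Wording only, but not free in power. For paired-t outcomes at n = 20 the detectable dz rises from 0.66 to 0.84 at the first Holm step with five primaries (0.82 with four), which uses part of the margin that section D keeps for smaller effects or greater variability. With 10 exercise completers, power at 0.01 would be 0.36-0.66 at the back-solved dz. Bubble scores and core temperature have no stated effect size, so their power after the split must be calculated, and it cannot be said that they would need no extra subjects.
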